3.2 Secondary Objectives

- Pharmacokinetics of glyburide following acute cervical SCI: Plasma concentrations will be serially quantified through day 3 following SCI. Comparisons will be made to reported levels achieved healthy patient cohorts
- Neurologic recovery following SCI: The neurologic status of patients will be assessed using the ASIA Impairment Scale (as assessed by ISNCSCI criteria) and the Spinal Cord Independence Measure (SCIM version III) [22]. The motor and sensory sub scores of the ASIA assessment will be determined on first contact,

every day until Day 4, at 1-2-4-6 weeks, and at 3-6-12 months of follow-up. The SCIM version III will be assessed at 3, 6 and 12 months of follow-up. Comparisons will be made to control subjects (with a 1:3 matching ratio in the NACTN registry matched based on age, co-morbidities, initial injury severity, and injury level.

- Serum biomarker levels: Standard enzyme-linked immunosorbent assay (ELISA) techniques will be used to measure blood levels of neurofilament light chain, neuron-specific enolase, tau, S100b, and glial fibrillary acidic protein levels on admission, at 24 hours and on days 3, and 7 following SCI. Comparisons will be made to (i) matched control serum values of non-treated subjects with acute cervical SCIs [23] and (ii) previously published values observed in non-treated control patients [24-26].
- Spinal cord lesion volumetric analysis: Standard sequences (T1, T2, FLAIR, SWI) at 3T field strength will be used to assess the extent of the hemorrhagic lesion and surrounding edema. Patients will be imaged on the day of admission and on day 2 following injury (standard-of-care studies). Volumetric assessments of lesion size (based on manual outlines) will be performed and compared at the two time-points by the study neuroradiologist to assess for the progression of intrinsic cord signal changes [27].

4.0 STUDY DESIGN

4.1 Inclusion/Exclusion Criteria

All patients with ASIA A, B or C acute traumatic spinal cord injuries will be assessed for suitability and prospectively enrolled in the study. Only cervical level (C2-C8) level injuries in patients aged 18 to 80 years old will be included. Detailed eligibility criteria are listed below.

The use of immunosuppressive therapy (including methylprednisolone and other corticosteroids) will be discouraged; however, use of such therapy will not require exclusion or discontinuation from the study. While once considered as an option for patients with acute SCI, it is noteworthy that more recent recommendations have all re-

evaluated the routine use of methylprednisolone [28]. The most recent guidelines published by a panel convened by the Joint Section on Spine and Peripheral Nerves of the American Association of Neurological Surgeons and Congress of Neurological Surgeons has in fact recommended against its use following acute SCI given its negative risk- benefit profile [3]. In the words of the panel: “Administration of methylprednisolone for the treatment of acute SCI is not recommended. Clinicians considering methylprednisolone therapy should bear in mind that the drug is not approved by the Food and Drug Administration for this application. There is no Class I or Class II medical evidence supporting the clinical benefit of methylprednisolone in the treatment of acute SCI. Scattered reports of Class III evidence claim inconsistent effects likely related to random chance or selection bias. However, Class I, II, and III evidence exists that high-dose steroids are associated with harmful side effects, including death.” Of note, the recent phase 1/2a riluzole study reported that corticosteroids were administered at the time of admission to only 39% of the patients (while 58% of historic NACTN registry patients had received this treatment) [4].

- **Inclusion Criteria:**

1. Age: ≥ 18 years and ≤ 80 years
2. Written informed consent by patient or legal authorized representative
3. No other life-threatening injury
4. No evidence of sepsis
5. Acute cervical SCI with ASIA Impairment Scale grade A, B or C on admission
6. Non-penetrating SCI at neurologic level from C2 to C8
7. Initiation of study drug within 8 hours of injury

- **Exclusion Criteria**

1. Unconsciousness or other mental impairment that prevents neurological assessment within the first 8 hours
2. Acute SCI with ASIA Impairment Scale grade D or E
3. Currently involved in another non-observational SCI research study or receiving another investigational drug
4. History of hypersensitivity to sulfonylureas, in particular glyburide, or any of its components

5. Other illness (including mental disorder) that could preclude accurate medical and neurological evaluation (at discretion of the site investigator)
6. Unable to commit to the follow-up schedule
7. A recent history of regular substance abuse (illicit drugs, alcohol), which in the opinion of the investigator would interfere with the subject's participation in the study
8. Any condition likely to result in the patient's death within the next 12 months
9. Prisoner
10. Severe renal disorder from the patient's history (e.g. dialysis) or baseline eGFR of $< 30 \text{ mL/min/1.73 m}^2$
11. Known severe liver disease, or ALT > 3 times upper limit of normal or bilirubin > 2 times upper limit normal. Subjects may be randomized if liver function tests have been drawn but are not yet available and the subject has no known history of liver disease; however, treatment with glyburide will be discontinued prior to the second dose if liver function tests indicate ALT > 3 times upper limit of normal or bilirubin > 2 times upper limit of normal
12. Blood glucose $< 55 \text{ mg/dL}$ at enrollment or immediately prior to administration of glyburide, or a clinically significant history of hypoglycemia
13. Acute ST elevation myocardial infarction, and/or acute decompensated heart failure, and/or QTc $> 520 \text{ ms}$, and/or known history of cardiac arrest (PEA, VT, VF, asystole), and/or admission for an acute coronary syndrome, myocardial infarction, or coronary intervention (percutaneous coronary intervention or coronary artery surgery) within the past 3 months
14. Known treatment with Bosentan within past 7 days
15. Known G6PD enzyme deficiency
16. Pregnancy: Women must be either post-menopausal, permanently sterilized or, if ≤ 50 years old, must have a negative test for pregnancy obtained before enrollment
17. Breast-feeding women who do not agree to stop breast-feeding during and for 7 days following the end of oral glyburide administration
18. Subjects who in the opinion of the investigator are not suitable for inclusion in the study (reason to be documented).

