4.4 Study-related management (non-standard of care)

Non-standard-of-care blood work will be obtained at the following time points following the SCI:

- Pharmacokinetic Analysis: Daily, baseline through Day 3
- Biomarkers Levels: Enrollment/Baseline, 24 hours, Day 3, and Day 7

Clinical, imaging, and safety assessments will be performed throughout the study period:

- Patients will be closely monitored clinically for all AEs during the first 28 days of the study. SAEs will be monitored for the entire duration of the study. For the initial hospitalization period, the incidence of AEs will be compared where possible to that of matched controls obtained from the NACTN registry (1:3 ratio with respect to age, co-morbidities, injury level, and injury severity). The 1:3 patient matching will be undertaken by the study statistician.
- Neurological evaluation will be carried out at specific time-points up to one year following SCI to assess for changes in neurological status. The 3, 6, and 12-month ISNCSCI motor/sensory and SCIM vIII scores of the patients will also be compared where possible to that of matched controls from the literature and from the NACTN registry.

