5.6 Prohibited Interventions

No sulfonylurea agents may be administered during the first 4 days of admission. Subsequently, it is preferable that no sulfonylureas be administered through study completion. However, use of sulfonylureas starting beyond Day 4 will not result in study discontinuation.

The use of therapeutic steroids or hypothermia (cooling to below 36 Celsius) is discouraged for treatment of the patient's acute SCI. If the patient requires steroid therapy for the treatment of another condition, this is allowable.

No other investigational drugs may be administered during the study follow-up period. Decisions on whether to withdraw the patient from the study will be made on a case-by-case basis should another investigational drug nevertheless have been administered.

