7.0 STATISTICAL CONSIDERATIONS

Descriptive statistics will be generated for all variables of interest. Categorical measures will be reported with frequencies and percentages and continuous measures with means and standard deviations. The frequency of AEs will be reported (as captured on the modified NACTN form) and, where possible, will be compared to those of the matched controls (along with corresponding confidence intervals). We will match study patients and the historical NACTN cohort data on criteria including: age, co-morbidities, injury level, and injury severity (ASIA A, B or C SCI). Additionally, the number of patients who were otherwise eligible for the study but did not enroll due to lack of infusion within 6 hours will be reported. Secondarily, matched tests will be utilized to compare neurologic outcomes between those receiving glyburide and matched historical controls.

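### The NACTN matching criteria never name corticosteroid use at admission, a foreseeable imbalance that could make glyburide look safer in the non-metabolic adverse-event and mortality comparisons

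*Combined protocol and SAP*

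**What the plan says.** The treated group (up to 10 patients) is compared with NACTN registry patients at 1:3, so with at most 30 controls. Under the primary safety objective (section 3.1), the frequency of adverse events and all-cause and cardiac mortality are set against these controls. Section 3.2 uses the same source for neurologic recovery.

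The matching factors are stated three times:
- Section 3.2: "matched based on age, co-morbidities, initial injury severity, and injury level".
- Section 4.4: "1:3 ratio with respect to age, co-morbidities, injury level, and injury severity". The matching is left to the study statistician.
- Section 7.0: "We will match study patients and the historical NACTN cohort data on criteria including: age, co-morbidities, injury level, and injury severity".

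Corticosteroids are dealt with elsewhere. Section 4.1 says that immunosuppressive therapy, steroids included, "will be discouraged; however, use of such therapy will not require exclusion or discontinuation from the study". Section 5.6 repeats: "The use of therapeutic steroids or hypothermia (cooling to below 36 Celsius) is discouraged" as treatment for the acute injury, while steroids needed for another condition are allowed. Section 4.1 cites guidance that "Class I, II, and III evidence exists that high-dose steroids are associated with harmful side effects, including death". It then reports that in the riluzole trial, which section 2.1 attributes to the NACTN group, "corticosteroids were administered at the time of admission to only 39% of the patients", "while 58% of historic NACTN registry patients had received this treatment".

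No section plans stratification, adjustment, a sensitivity analysis or a between-group report for steroid use.

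**The concern.** The protocol names a co-treatment as potentially harmful, reports it as common in the control source, discourages it in the treated group, and does not list it among the matching factors. Steroid use is not an eligibility criterion, so applying the trial's eligibility rules to the registry would not remove the difference.

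If controls had more steroid exposure and steroids raise the rate of complications, the controls would show more infections or deaths for a reason unrelated to glyburide. The treated group would then look safer than it is, and a real excess of drug-related events could be partly hidden. For a safety pilot meant to inform a phase II/III design, that is the unfavourable direction of error. The confidence intervals planned in section 7.0 describe random error only, and adding controls from the same source would not shrink this bias.

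**Working it through.** The documents give no calculation on this point to reproduce, and the 58% and 39% come without counts. As a side check, Table 4 in section 6.2 is internally consistent: 285/1376 = 20.7% and 18/485 = 3.7%.

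**Inputs from the documents**
- Steroid exposure: 58% in historic registry patients, 39% in the riluzole trial (section 4.1).
- Registry incidence: infection 33.2%, death 3.7% (Table 4).
- Group sizes: 10 treated and 30 controls.

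**Assumptions**
- The 58% applies to the controls eventually matched, and to the patients behind Table 4.
- Steroid use in this trial, t, runs from 0% to 39%. The plan gives no expected figure.
- The relative risk (RR) of infection with steroids is 1.0, 1.25, 1.5 or 2.0. The documents give none.
- Glyburide itself has no effect.

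**Exposure gap.** 58 − 39 = 19 points at one end, 58 − 0 = 58 points at the other. Among 30 controls, 30 × 0.58 = 17.4 would be expected to have had steroids.

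**Spurious difference in infection.** With P = 0.332, the risk without steroids is p0 = P / (0.42 + 0.58 × RR). The expected treated-group rate is p0 × ((1 − t) + t × RR), and the bias is that rate minus P.

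| RR | p0 | Bias at t = 0% | Rate at t = 39% | Bias at t = 39% |
|---|---|---|---|---|
| 1.0 | 33.2% | 0 | 33.2% | 0 |
| 1.25 | 0.332/1.145 = 29.0% | −4.2 points | 31.8% | −1.4 points |
| 1.5 | 0.332/1.290 = 25.7% | −7.5 points | 30.8% | −2.4 points |
| 2.0 | 0.332/1.580 = 21.0% | −12.2 points | 29.2% | −4.0 points |

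At t = 58% the bias is zero for every RR; above that it changes sign.

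**Mortality.** The same formula with P = 0.037 and RR from 1.25 to 2.0 gives −0.2 to −1.4 points.

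**Precision, ignoring matching.** SE = sqrt(P(1 − P)(1/10 + 1/30)). For infection this is sqrt(0.332 × 0.668 × 0.1333) = 0.172, or about 17 points, with a 95% half-width of about 34. For death it is about 7 points. The bias is below one standard error in every cell.

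**Neurologic outcomes.** An assumed steroid effect of 0.1 to 0.3 SD, of either sign, multiplied by the exposure gap shifts the comparison by 0.06 to 0.17 SD at t = 0% and 0.02 to 0.06 SD at t = 39%. The standard error is sqrt(1/10 + 1/30) = 0.37 SD.

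**Would the imbalance show itself?** A two-sided 5% comparison of steroid use in 10 versus 30 patients has power of about 99% if t is close to 0%, 83% at 10%, 56% at 20% and 17% at 39%. At the smaller gap, a non-significant test would not be evidence of balance.

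**The case against.** The strongest reply is that noise dominates. With 10 treated patients the interval for infection spans roughly ±34 points, the analysis is descriptive, the comparisons are promised only where possible, and section 10.0 itself asks for caution. This stands as a limit on importance, and the feasibility objective is untouched. It does not remove the point: the intervals do not include this bias, and a reader cannot allow for an imbalance that is not reported.

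Second, section 7.0 introduces its factors with the word including, so the statistician could add steroid use. That also stands: the factor is unnamed, not excluded. But sections 3.2 and 4.4 give the same four factors with no such opening, and a choice made after outcomes are known would be weaker than one made now.

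Third, the evidence for direction is limited. The quoted guidance concerns high doses, while the 58% and 39% describe any corticosteroid at admission, with no dose stated. The 58% may not hold among cervical ASIA A–C registry patients. Steroids are allowed here, so t = 0% is only a bound and use could exceed 39%. All of this stands, which is why the result is a range that includes zero.

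Three stronger readings are tempting and not supported:
- A reader might infer that steroid effects on glucose push the metabolic comparison the same way. The documents state no such effect. The glucose outcomes in section 3.1 concern low values, so if steroids did raise glucose, controls would have less hypoglycemia and glyburide would look worse. Table 4 as shown has no metabolic row.
- A reader might infer a known bias in neurologic recovery. Section 4.1 reports no Class I or II evidence of steroid benefit and only inconsistent Class III effects, so neither sign nor size follows.
- A reader might multiply 42% by 485 and conclude that about 204 steroid-free controls exist. The two figures come from different cited sources, and the number of eligible cervical ASIA A–C patients is not given.

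**Conclusion.** The point holds as a cheap improvement. None of the three statements of the matching criteria names corticosteroid use, although the protocol's own figures and steroid policy make an imbalance foreseeable. If it occurs and steroids raise complication rates, the non-metabolic adverse-event and mortality comparisons would tilt in glyburide's favour. For neurologic outcomes the direction is open, and no claim is made for hypoglycemia.

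For infection the tilt is about 1 to 12 points, against a standard error of about 17, and zero if steroids carry no extra risk. That range rests on assumed relative risks, on the 58% applying to the matched controls, and on trial use of 0 to 39%. An imbalance is expected, not certain. The omission affects how the historical comparison is read and does not invalidate the study.

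**What to change.** In sections 3.2, 4.4 and 7.0, add corticosteroid use at admission, before the first glyburide dose (yes/no), as a matching factor. The timing matters: steroids given later, including those section 5.6 allows for other conditions, could follow from events after treatment starts, and matching on them would condition on post-treatment exposure. Where the match on this factor is exact, the bias from this source is zero by construction.

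If too few eligible cervical ASIA A–C controls allow exact matching, keep the four-factor match, report steroid use in both groups, and add a sensitivity comparison restricted to or stratified by steroid status. Present the two proportions as they are, without relying on a significance test for balance. Decide between the two routes before outcomes are compared.

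The cost is one binary variable, with no patient burden and no change to any clinical rule. The trial already records concomitant medications (sections 5.4 and 5.8). The 58% figure suggests that the registry holds the variable, but patient-level availability should be confirmed. The downside is a smaller control pool and slightly looser matching on age or co-morbidity.

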3.0 OBJECTIVES

3.1 Primary Objectives

- **Feasibility:** To assess the feasibility of running a larger phase II or III study among this population of patients where treatment must begin within a defined time frame. The number of patients who would otherwise be eligible for the study but did not receive study treatment within the 8-hour time frame will be recorded (ratio of recruited versus screened). The rate of recruitment will also be recorded.
- **Safety:** Vital signs, clinical exams, ECG, and clinical laboratory results will be carefully and continuously monitored during the course of hospitalization. Adverse events (AEs) will be assessed throughout the course of hospitalization through Day 28. In addition to presenting a summary of all AEs, where possible, a comparison of AEs occurring in study subjects vs. those occurring in matched historical controls (as captured in the NACTN registry) will be made. To facilitate this comparison, AEs will be grouped into one of 10 systems according to a modified NACTN chart [20, 21] (see appendix 1): cardiac, pulmonary, hematology, gastrointestinal/genitourinary, infections, skin, failure of stabilization, neuropsychiatric, hypoglycemia/other metabolic, and other. These AEs will be described further with respect to the specific name of the event (that is, the “type” of event; for example, for cardiac events, the type could be bradycardia or other dysrhythmia, cardiac arrest, etc.). Severity (“intensity”, as per the NACTN chart) as well as relatedness to glyburide will also be assessed. The frequency of AEs, as well as mortality (all-cause and cardiac-related), will be compared to that of a matched cohort from the NACTN registry [20, 21].

Specific outcome variables related to assessing blood glucose (BG)-related safety of glyburide are:

- Hypoglycemia (i.e. Blood Glucose (BG) < 55 mg/dL
- Symptomatic hypoglycemia i.e. hypoglycemia with investigator-identified hypoglycemic symptoms.

The following table defines which BG values should be reported as AEs:

Table 1: Blood Glucose Values and AE reporting

BG Value	Report as AE?
70-79 mg/dL	Mandatory AE reporting not required; may be reported as an AE (and coded appropriately in terms of severity) if the event meets the protocol-defined definitions.
55- 69 mg/dL	Must be reported as an AE, if confirmed by a point-of-care or lab value retest (and coded appropriately in terms of severity)

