5.3 Registration Process

To register a patient, the following documents should be completed and uploaded to the electronic data capture system (REDCap) by the research team:

- Copy of required clinical and radiologic tests
- Signed patient consent form
- HIPAA authorization form
- Eligibility Screening Worksheet
- Registration Form

Eligible patients will be enrolled within the first 8 hours after documented trauma, so that oral glyburide administration can begin no later than 8 hours after injury. This injury-to-drug timeframe appears feasible given the injury-to-admission times reported in recent SCI studies. For instance, in the phase 1/2a Riluzole study [4], the mean injury-to-admission time was 3.0 ± 1.8 hours (median 2.3 hours). The median injury-to-drug time of 8.5 hours in that study likely reflects the time taken for additional MRI studies (in addition to CT imaging).

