5.5 Study Drug Description, Dose, and Administration

Enrolled patients will receive 12 doses of glyburide starting within 8 hours of SCI. The dosing regimen involves an initial dose of 1.25 mg followed by eleven consecutive doses of 0.625 mg every 6 hours. The total daily dose of glyburide on Day 1, Day 2 and Day 3 will be 3.125 mg, 2.5 mg, and 2.5 mg respectively (see Table 2).

Table 2: Study Dosing

	Day 1	Day 2	Day 3
Total Dose	3.125 mg	2.5 mg	2.5 mg
	First dose of 1.25 mg then 0.625 mg every 6 hours	0.625 mg every 6 hours	0.625 mg every 6 hours

This injury-to-drug timeframe will apply to patients managed non-operatively as well as to patients undergoing surgery (likely a majority of patients in the trial). Drug administration should not be stopped as the standard of care diagnostic studies and treatment is provided, including if the patient is transferred to the OR for decompression and stabilization. Hard stop rules for glyburide administration are listed below.

In the event a dose of glyburide is missed (beyond 2.5 hours from the expected administration time), the next dose should be administered at 1.25 mg followed by the usual 0.625 mg dose for subsequent administrations. If the missed dose is acknowledged within 2.5 hours of the expected administration time the dose should be given and the deviation noted.

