5.7 Interventions Related to Blood Glucose

- **Insulin**

Insulin is not permitted during the period of study drug administration when BG < 120 mg/dL. "Tight" BG control (80 – 110 mg/dL) is not permitted during the period of study drug administration.

- **Supplemental Fluids**

Supplemental fluids are to be standard of care except that during glyburide administration, D5NS or D10NS must be used instead of NS if necessary to maintain BG above 80 mg/dL. Total fluid volume should be consistent with site clinical practice and the clinical status of the subject.

- **Hypoglycemia treatment**

Any BG of < 70 mg/dL must be promptly treated with a bolus of D50W at a volume (ml) of $(100 - \text{BG in mg/dL}) \times 0.4$ as per Juneja et al. 2009 [31]. If supplemental fluids are NS, D5NS should be started. If supplemental fluids are D5NS, D10NS should be substituted. All BG < 70 mg/dL also should preferably be verified by laboratory testing, but repeat point-of-care tests may be used as well. To avoid false readings, blood for the repeat test must be drawn prior to treatment with D50W or switching supplemental fluids.

- **Glyburide Dose Reduction**

Glyburide dosing must be reduced if subject is being administered D5NS or D10NS and (i) there is one confirmed BG < 55 mg/dL; or (ii) there are three confirmed BG < 70 mg/dL within a 12-hour period. If (i) or (ii) above occurs and the subject is on NS, D5NS or D10NS must first be started. If criteria (i) or (ii) are still met, then glyburide dosing should be adjusted to every 8 hours until three consecutive blood glucose readings of >70 are noted. If appropriate levels of BG are not reached within 8 hours of the first dose reduction, the next dose of glyburide should be skipped as an additional dose reduction. Glyburide dosage must only be adjusted based on verified laboratory or repeat point-of-care test values that are taken 15 minutes or more following the last administration of insulin.

- **Glyburide Discontinuation**

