5.8 Days 1-7 (0-168 hours)

- The first dose of glyburide must be administered within 8 hours of injury and stopped after 72 hours. Hard stop rules for glyburide administration are listed below.
- As per recommended standard-of-care guidelines [3], subjects will be admitted to the intensive care unit following initial diagnostic testing where continuous respiratory, cardiac, and hemodynamic monitoring will be undertaken [32]. Maintenance of normal blood oxygenation and a mean arterial blood pressure of 85-90 mmHg will be emphasized in this monitored setting continuously over the first full 7 days following injury.

- The following assessments will be performed through day 7 following injury (during and after study drug regimen):
 - Safety labs: 24 hours (± 12 hours), 48 hours (± 12 hours) 72 hours (± 12 hours) and 96 hours (± 12 hours).
 - Hematology: complete blood count
 - Chemistry: electrolytes (sodium, potassium, chloride, bicarbonate), BUN, creatinine
 - Liver Function Tests: AST, ALT, bilirubin (total and direct), and alkaline phosphatase
 - Blood glucose (BG) monitoring will be hourly (± 30 minutes) for Hours 1-24, every 2 hours (± 30 minutes) for Hours 25-48 and every 4 hours (± 60 minutes) for Hours 49-88. If BG < 70 mg/dL, BG monitoring is required every 15 (± 10 minutes) minutes until BG ≥ 80 for 3 consecutive readings without exogenous bolus glucose supplementation, then hourly (± 30 minutes) for the next 12 hours and every 2 hours (± 30 minutes) thereafter.
 - Continuous bedside cardiac telemetry monitoring from Hour 0 through Hour 72
 - ECG (12-lead) at 4-6 hours, 24 \pm 6 hours, 48 \pm 6 hours and 60-72 hours (from the start of study drug regimen). The ECGs will be read within 12 hours, recorded as clinically significant or non-clinically significant, and signed off on by study team member.
 - Blood sampling for PK prior to dosing, at 4-6 hr (prior to the second study drug administration), 24 \pm 6 hours, 48 \pm 6 hours and 60-72 hours.
 - PK Samples to be drawn as close as possible to ECGs
 - Start time of drug and time of subsequent dosing. Record reason for any missed doses.
 - Concomitant medications and procedures/therapies
 - Review safety and AEs

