5.11 Study Calendar

Test and Observations	Screening / Enrollment (up to 6 hours prior to treatment)	Day 1	Day 2	Day 3	Day 4	Day 7	Day 14 or D/C	Day 28 (+/- 7 days)	Day 42 (+/- 7 days)	Day 84 (+/- 14 days)	Day 182 (+/- 14 days)	Day 365 (+/- 30 days)
History & Physical	X											

Vital Signs ^a	X												
Consent	X												
Demographic ^b	X												
Operative Data ^f							X						
Length of Stay							X						
Adverse Events ^k	X	X	X	X	X	X	X	X	X	X	X	X	X
Pregnancy Test ^d	X												
SCI (Cervical) ^e	X												
Inclusion/Exclusion	X												
Concomitant Review	X	X	X	X	X	X	X	X					
Procedures	X												
MRI	X		X										
CT	X												
Labs ^c	X	X	X	X	X		X						
ECG(12-lead)	X	X	X	X									
Drug													
Drug Administration ^{i,j}	X	X	X	X									
Serum Biomarkers ^h	X	X		X		X							
Pharmacokinetic ^g	X	X	X	X									
Outcome Measures													
AIS	X	X	X	X	X	X	X	X	X	X	X	X	X
SCIM vIII										X	X	X	

- a. Temperature, blood pressure, pulse, O₂, respiration, BMI, height and weight (can be estimated if patient cannot be measured). Vitals are to be collected at screening (prior to enrolment).
- b. Demographics: age, race, and gender.
- c. Labs: hematology (complete blood count); chemistry (sodium, potassium, chloride, creatinine, electrolytes, bicarbonate, bun); liver function (AST, ALT, bilirubin total, bilirubin direct, and alkaline phosphatase); blood glucose (Blood glucose (BG) monitoring will be hourly (± 30 minutes) for Hours 1-24, every 2 hours (± 30 minutes) for Hours 25-48 and every 4 hours (± 60 minutes) for Hours 49-88. If BG < 70 mg/dL, BG monitoring is required every 15 (± 10 minutes) minutes until BG ≥ 80 for 3 consecutive readings without exogenous bolus glucose supplementation, then hourly (± 30 minutes) for the next 12 hours and every 2 hours (± 30 minutes) thereafter)
- d. Pregnancy test (only complete if woman is of childbearing potential).
- e. SCI (cervical): time, cause, and level of injury.
- f. Optional: only required if patient has surgery.
- g. Blood sampling for PK prior to dosing, at 4-6 hr. (prior to the second dose of glyburide (glyburide), 24±6 hours, 48±6 hours and 60-72 hours. PK samples to be drawn as close as possible to ECGs.
- h. Serum biomarkers: enrollment/baseline, 24 hours, Day 3, and Day 7.
- i. Cannot continue until enrollment liver function test are available and indicate ALT ≤ 3 X upper limit of normal and Bilirubin ≤ 2 X upper limit of normal

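### The 1.25 mg first dose may be given at a pre-dose glucose of 55-69 mg/dL, and no text makes it wait for recovery

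*Combined protocol and SAP*

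**What the plan says.** All references are to the combined protocol and SAP.

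- **Eligibility (4.1, exclusion 12).** A BG below 55 mg/dL bars the patient "at enrollment or immediately prior to administration of glyburide, or a clinically significant history of hypoglycemia". A value of 55-69 does not.
- **Dose (5.5).** The regimen is "an initial dose of 1.25 mg followed by eleven consecutive doses of 0.625 mg every 6 hours". After a missed dose, the next one is again 1.25 mg.
- **Timing.** Section 5.4 wants the drug given as early as possible once the patient is enrolled. Section 5.8 sets the limit at 8 hours from injury.
- **Treatment of low glucose (5.7).** "Any BG of < 70 mg/dL must be promptly treated with a bolus of D50W". On fluids: "If supplemental fluids are NS, D5NS should be started. If supplemental fluids are D5NS, D10NS should be substituted". During glyburide administration, dextrose-containing fluid is to keep BG above 80, and insulin is not allowed below 120.
- **Rechecks.** After a BG below 70, footnote c of the study calendar (5.11) says "BG monitoring is required every 15 (± 10 minutes) minutes until BG ≥ 80 for 3 consecutive readings". Section 5.8 counts only readings of at least 80 "for 3 consecutive readings without exogenous bolus glucose supplementation". Footnote c belongs to the Labs row, which is marked at Screening/Enrollment, so the rechecks can be read as covering the time before the first dose.
- **Reporting (3.1, Table 1).** For 55-69: "Must be reported as an AE, if confirmed by a point-of-care or lab value retest".
- **Judgment and escalation.** Exclusion 18 lets the investigator decline an unsuitable patient. Section 5.2 sends matters that would delay treatment to the study principal investigator.

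**The concern.** The plan treats 55-69 mg/dL as a state that needs prompt correction, yet it lets a glucose-lowering drug be started in that state at the largest scheduled dose. A site that follows the text could give 1.25 mg while it is still treating low glucose, and the timing instructions push it to dose early. An oral dose cannot be taken back: Section 2.2 puts the peak at about four hours and the terminal half-life at about 10 hours.

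Patient safety is what is mainly at stake. Interpretation is affected as well. Glucose safety is part of the primary safety objective, and a confirmed BG below 55 is reported as an SAE. With 10 patients, one such event is 10% of the sample. If it followed a dose given at an already low glucose, it would be hard to attribute to the drug.

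**Working it through.** **1. Reproduce the plan's dose figures (5.5, Table 2).** Day 1: 1.25 + 3 × 0.625 = 3.125 mg. Days 2 and 3: 4 × 0.625 = 2.5 mg each. Total: 3.125 + 2.5 + 2.5 = 8.125 mg, which equals 1.25 + 11 × 0.625. The stated figures are correct. The first dose is 1.25/0.625 = 2.0 times a maintenance dose and 1.25/3.125 = 40% of Day 1.

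**2. Set the thresholds side by side.** The D50W volume in 5.7 is (100 − BG) × 0.4 mL.

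| Pre-dose BG (mg/dL) | Excluded (below 55)? | D50W required (below 70)? | Volume |
|---|---|---|---|
| 54 | yes | yes | not dosed |
| 55 | no | yes | 45 × 0.4 = 18.0 mL |
| 69 | no | yes | 31 × 0.4 = 12.4 mL |
| 70 | no | no | none |

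The band where treatment is required but dosing is permitted is exactly 55-69.

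**3. Look for a hold on the first dose.**
- The treatment rule in 5.7 sets glucose and fluids and does not mention dosing.
- The 15-minute rechecks are a monitoring rule.
- Dose reduction (5.7) needs one confirmed BG below 55, or three confirmed below 70 in 12 hours. Its first effect is to space later doses to every 8 hours.
- Discontinuation (5.7, 6.4) needs an earlier reduction.
- The calendar's one laboratory-based hold (footnote i) concerns liver tests.

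None of these delays the first dose at 55-69.

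**4. How often it might arise.** The documents give no rate for a pre-dose BG of 55-69. Section 2.0 cites a series in which 53% were hyperglycemic on admission, so low values are probably uncommon. I assume a per-patient rate p between 0.1% and 2%, with no documentary basis. The chance of at least one case in 10 patients is 1 − (1 − p)^10:
- p = 0.1%: 1.0%
- p = 1%: 9.6%
- p = 2%: 18.3%

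The expected number is 10p, or 0.01 to 0.2 patients.

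**5. What a hold takes from the 8 hours.** Section 5.3 cites a riluzole study with injury-to-admission time of mean 3.0 h, SD 1.8 h and median 2.3 h. Minutes left = 480 − 60 × hours to admission.

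| Admission | Minutes left | 15 min | 30 min | 45 min |
|---|---|---|---|---|
| 2.3 h (median) | 342 | 4.4% | 8.8% | 13.2% |
| 3.0 h (mean) | 300 | 5.0% | 10.0% | 15.0% |
| 4.8 h (mean + 1 SD) | 192 | 7.8% | 15.6% | 23.4% |

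These shares flatter the fix, because the clock starts at admission and CT, consent and laboratory work come out of the same minutes. The same study had a median injury-to-drug time of 8.5 hours, which is 30 minutes beyond this trial's limit. Section 5.3 attributes that to additional MRI, which this trial does not require before dosing. Real slack may be much less than 192-342 minutes.

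**The case against.** The best defense is that 55 is a deliberate and consistent cut-off. It defines hypoglycemia as an outcome, marks the SAE level, and is the single-value trigger for dose reduction. At 55-69 the plan's approach is to give glucose and continue the drug. A reader might infer from the 55/70 split that the protocol contradicts itself. It does not: the exclusion and the treatment rule answer different questions. This part of the objection stands, and the exclusion should stay at 55.

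A second argument is that the first dose is not singled out. One might infer that later doses are protected at 55-69 and only the first is exposed. The documents do not support that, because a single reading of 55-69 does not hold a later dose either, and the 1.25 mg dose can recur after a missed dose. The case for a rule at 1.25 mg is narrower: it is twice the maintenance dose, and a recovery check is easiest to apply before the drug has been started.

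Third, the benefit is not quantified. Against a peak at about four hours, a 15-minute shift is small, and hourly checks for Hours 1-24 already span the peak. That is fair, and it keeps the point modest. It does not remove it, since those measures respond to low glucose without asking whether the dose should go in.

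Finally, every minute matters. Section 2.0 reports that none of 16 patients screened for the earlier intravenous study was eligible. This is a good reason to keep the hold short.

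**Conclusion.** The gap is real and worth closing. It is a modest, probably rare safety gap with a cheap remedy. That the dose is permitted at 55-69 with no hold follows directly from the text. How often it would happen rests on the assumed 0.1% to 2%, and the documents do not allow the harm avoided to be estimated.

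Two stronger readings should be resisted. A reader might infer that such a patient would go untreated or unwatched before dosing. Section 5.7 applies to any BG below 70, and footnote c supports rechecks from screening onward. A reader might also infer that every center would have to settle the matter alone. Section 5.2 gives a site considering a delay a route to the study principal investigator, and exclusion 18 lets the investigator decline the patient. However, neither provision contains a glucose criterion, and exclusion 18 loses a patient whom a brief hold could keep.

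**What to change.** Keep exclusion 12 at 55 and add one rule to Sections 5.5 and 5.7, for example:

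> If BG immediately before the first 1.25 mg dose, or before a repeat 1.25 mg dose after a missed dose, is 55-69 mg/dL, treat per 5.7 and hold that dose. Release it when a recheck on the 15-minute schedule of 5.8, taken after the D50W bolus with dextrose fluid running, is at least 80 mg/dL. Continue the 5.8 checks after dosing. The first dose must still start within 8 hours of injury; if recovery is not reached by then, do not dose, and record low glucose as the reason.

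The 80 mg/dL target and the 15-minute schedule come from the protocol. Accepting one post-bolus reading does not: it is looser than the three bolus-free readings of 5.8, and is chosen to protect the 8-hour window. The schedule's tolerance of ± 10 minutes allows a recheck at 5 to 25 minutes, so a single reading may partly reflect the bolus. That is why the checks must continue after dosing.

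The rule needs no new test or equipment. It costs about 15 minutes or more in affected patients only, and occasionally a patient near the 8-hour limit. Such a loss would count against the primary feasibility outcome; the recorded reason keeps that count interpretable.
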